Study Protocol and Statistical Analysis Plan

Official Title:

Evaluation of Observation Periods and Biphasic Reaction Risk Factors in Pediatric Anaphylaxis Cases in the Pediatric Emergency Department: A Retrospective Study

Brief Title:

Observation Periods and Biphasic Reaction Risk Factors in Pediatric Emergency Anaphylaxis Cases

Unique Protocol ID:

ADUPEDANAPH

NCT Number:**Responsible Party / Principal Investigator:**

Assoc. [name]. [name]

Department of Pediatrics (Emergency and Intensive Care)

Adnan Menderes University Faculty of Medicine, Aydın, Turkey

Co-Investigators:

- Dr. Öğr. Üyesi [name]
- Dr. Öğr. Üyesi [name]
- Uzm. [name] [name]

Ethics Approval:

Approved by the Clinical Research Ethics Committee of Adnan Menderes University Faculty of Medicine (Approval Date: 24/09/2025).

Document Date: 03 October 2025

1. Study Rationale

Anaphylaxis is a severe, rapidly developing systemic allergic reaction that poses unique challenges in pediatric emergency care. International guidelines recommend observation after treatment due to the risk of biphasic reactions (recurrence within 1–72 hours), but the optimal observation period in children is uncertain. Limited data exist from Turkey regarding pediatric anaphylaxis triggers, treatment practices, biphasic reaction frequency, and risk factors.

2. Objectives

- **Primary Objective:**

To determine the average observation period in the pediatric emergency department for children presenting with anaphylaxis and to evaluate the frequency and timing of biphasic reactions.

- **Secondary Objectives:**

- To analyze independent risk factors for biphasic reactions, including delayed epinephrine administration, asthma history, and severity at presentation.
- To assess the rate of hospital admission and need for intensive care.
- To describe treatment patterns (use and timing of epinephrine, corticosteroids, antihistamines, fluids) in the emergency setting.

3. Hypotheses

H1: Early administration of intramuscular epinephrine reduces the risk of biphasic reactions and improves clinical outcomes.

H2: A history of asthma and severe initial clinical presentation are associated with higher risk of biphasic reactions and prolonged observation requirements.

H3: Children requiring multiple doses of epinephrine are at increased risk for hospitalization and biphasic reactions.

4. Study Design

Type: Observational

Design: Retrospective analytic cohort (chart review)

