Setting: Pediatric Emergency Department, Adnan Menderes University Hospital

Period: January 1, 2014 – December 31, 2024

Sample: All consecutive patients <18 years diagnosed with anaphylaxis

5. Study Population

Inclusion Criteria:

- Children aged 0–18 years
- Diagnosis of anaphylaxis according to WAO 2020 criteria
- Complete medical records available

Exclusion Criteria:

- Incomplete or missing medical records

- Cases not meeting WAO 2020 diagnostic definition
- Isolated urticaria or localized allergic reactions

6. Methods

Data Sources: Patient files and electronic medical records (January 2014 – December 2024).

Variables collected:

- Demographics (age, sex)
- Medical history (comorbidities such as asthma, allergic diseases)
- Triggers (food, drug, insect sting, idiopathic)
- Clinical manifestations (skin, respiratory, cardiovascular, gastrointestinal, neurological)
- Treatments (IM epinephrine, time to first dose, number of doses, IV antihistamines, IV corticosteroids, fluid therapy, inhaled therapy)
- Duration of ED observation, hospitalization, ICU stay
- Occurrence and timing of biphasic reactions
- Outcomes: discharge, readmission, mortality (if any)

7. Statistical Analysis Plan

- **Software:** SPSS v20.0
- **Descriptive statistics:** Continuous variables will first be tested for normality (e.g., Shapiro-Wilk test). Normally distributed variables will be presented as mean \pm SD, while non-normally distributed variables will be expressed as median (IQR). Categorical variables will be summarized as n (%).
- **Comparisons:** Chi-square or Fisher's exact test for categorical variables; Student's t-test or Mann-Whitney U test for continuous variables, depending on distribution.
- **Regression analysis:** Logistic regression to identify independent predictors of biphasic reactions and prolonged observation (candidate variables: time to epinephrine, asthma, severity, multiple epinephrine doses).
- **Significance level:** $p < 0.05$ considered statistically significant.

Sample size: All eligible patients.

8. Ethical Considerations

- Approved by Adnan Menderes University Faculty of Medicine Clinical Research Ethics Committee (Approval No: 2025/266).

- Retrospective study design → no informed consent required.
- All data anonymized and stored securely.

9. Expected Contribution

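### The prolonged-observation model is offered repeat dosing and time to epinephrine as well as H2's baseline factors, which can dilute the severity association and, on one timing definition, make delay predict stay by construction

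*Combined protocol and SAP*

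**What the plan says.** The regression paragraph of Section 7 (Statistical Analysis Plan) reads "Logistic regression to identify independent predictors of biphasic reactions and prolonged observation" and attaches a single list to both outcomes: "candidate variables: time to epinephrine, asthma, severity, multiple epinephrine doses". It gives no selection or forced-entry rule, no cut-off for a prolonged stay, and no separate model without treatment variables.

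The three hypotheses in Section 3 differ in what they ask:

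- The first, H1, is about early treatment and reads "Early administration of intramuscular epinephrine reduces the risk of biphasic reactions and improves clinical outcomes".
- The second, H2, is about factors present on arrival and reads "A history of asthma and severe initial clinical presentation are associated with higher risk of biphasic reactions and prolonged observation requirements".
- The third, H3, is about repeat dosing and reads "Children requiring multiple doses of epinephrine are at increased risk for hospitalization and biphasic reactions".

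Only H2 names prolonged observation. Repeat dosing is tied to hospitalization and biphasic reactions. Early epinephrine is tied to biphasic reactions and to clinical outcomes that are not listed.

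Section 6 (Methods) collects "Treatments (IM epinephrine, time to first dose, number of doses" and "Duration of ED observation, hospitalization, ICU stay", with no starting point for either clock. The only wording on when observation happens is in Section 1: "International guidelines recommend observation after treatment due to the risk of biphasic reactions". That describes guidelines and does not define a study variable.

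**The concern.** Asthma history and initial severity are fixed when the child presents. The number of epinephrine doses is not: it follows presentation, plausibly depends on severity, and plausibly lengthens the stay. If it is in the model, the severity coefficient describes only the part of the association that does not run through repeat dosing. H2 makes no such restriction.

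Time to first dose raises a different problem. If stay is counted from arrival and the delay falls inside that interval, delay is a component of the outcome. It can then predict a long stay even when it has no bearing on what happens after the dose.

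Observation length is part of the primary objective, and Section 9 expects the results to inform practice. A severity association reported as weak or absent, or a delay association produced by the definition of stay, would mislead that use.

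**Working it through.** The documents give no sample size, event rate, stay distribution or power, so there is no plan figure to reproduce. Every input below is an assumption; the results show direction and range, not a forecast.

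**1. Dilution through repeat dosing**

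Let S be severe presentation and M repeat dosing. Stay in hours is T = constant + a·S + b·M + error, with error SD 2 h, N = 200 and 30% severe. Prolonged means above the median. The severe-versus-other difference in mean stay is a + b × [P(M|S=1) − P(M|S=0)], and the second term is the part that runs through repeat dosing.

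| Setting | Total difference | Share through M | Severity OR without → with M | Power without → with M |
|---|---|---|---|---|
| Strong links: a = 0.5, b = 3, M 40% v 10% | 0.5 + 3 × 0.30 = 1.4 h | 0.9/1.4 = 64% | about 2.6 → 1.5 | about 85% → 20% |
| Strong links, larger direct effect: a = 1.5 | 1.5 + 0.9 = 2.4 h | 0.9/2.4 = 38% | 5.1 → 3.4 | 100% → 92% |
| Weak links: a = 1, b = 1.5, M 20% v 10% | 1 + 1.5 × 0.10 = 1.15 h | 0.15/1.15 = 13% | about 2.5 → 2.3 | about 83% → 73% |

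With the strong links and no direct effect (a = 0), the OR goes from 1.80 to 0.99.

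A second simulation generated a binary outcome directly (400,000 records, direct severity OR 1.5). With OR 4 on both links, the severity OR was 2.09 without the dose term and 1.49 with it. With OR 2 on both links it was 1.61 and 1.49. With either link absent there was no dilution.

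**2. Delay as part of the stay**

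Let D be the delay to first dose and P the post-dose stay, independent of D. If the clock starts at arrival, T = D + P, and each hour of delay adds an hour to T. For a cut at the median and normal P, the log OR per hour is roughly 4 × 0.399 / SD(P):

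- SD 1.5 h: 1.596/1.5 = 1.06, OR 2.9.
- SD 3 h: 1.596/3 = 0.53, OR 1.7.

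Simulation gave ORs of about 1.7–3.1 per hour. How often this reaches p < 0.05 depends mainly on how widely delays vary. With N = 200, median delay 15–30 min, SD(P) 1.5–3 h and log-normal delay:

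| Log-SD of delay | Samples with delay significant |
|---|---|
| 0.4 | about 6–35% |
| 0.6 | 9–77% |
| 0.8 | 18–98% |
| 1.0 | 36–100% |

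Counting stay from the first dose gave a rejection rate of 6% and OR 0.99. These fits used delay alone, not the plan's four-variable model.

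**3. Delay and the severity estimate**

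Adjusting for delay does not dilute severity in the same way. With stay timed from arrival, mean delay 40 min and post-dose stay 1.2 times longer in severe cases, the severity OR was 2.05 without delay and 2.10 with it when all children were treated equally fast. When severe cases were treated in half the time, it was 1.60 without delay and 2.10 with it.

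**The case against.** - **The variables are only candidates.** Either epinephrine term may be absent from the final model. That is correct, so adjustment is possible rather than certain. But no selection rule is given: full entry keeps both terms, and selection on significance would tend to keep a strong mediator or a component of the outcome. The ambiguity does not remove the problem.
- **Mutually adjusted predictors are the stated aim.** Such a model is a legitimate answer to Section 7's wording. However, the Section 2 objective about independent risk factors concerns biphasic reactions. For observation, H2 states an association with baseline factors, which is a different estimand.
- **Unadjusted comparisons are planned.** They may show the crude severity association, so it need not vanish from the report. They name no groups and adjust for nothing, so they do not supply a baseline-adjusted H2 analysis.
- **The overlap of delay and stay is not established.** A reader might infer that both epinephrine variables fall inside the emergency department episode. The documents do not say so: time to first dose could run from symptom onset or include pre-hospital dosing, and observation could be timed from the first dose. This objection stands, so the coupling is conditional.
- **H1 may cover stay.** Its clinical outcomes are not listed, so the epinephrine terms should not simply be removed. This also stands and shapes the fix.

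**Conclusion.** The point holds as a risk in the specification. One candidate list serves two outcomes, and for prolonged observation it mixes H2's baseline exposures with treatment given after presentation. A model that includes repeat dosing can understate the severity association.

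The size ranges from minor (OR about 2.5 to 2.3) to decisive (about 2.6 to 1.5, with power falling from about 85% to 20%). It depends on how strongly severity drives repeat dosing and repeat dosing drives stay, and the documents give neither.

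A reader might conclude that H2's effect will be diluted, for asthma as well as severity, and by both epinephrine terms. The documents do not support that. Dilution needs both links, the argument applies to severity through repeat dosing, and adjusting for delay can raise the severity OR. The delay artefact arises only if stay is timed from before the first dose and contains the delay; its frequency then rests on an assumed spread of delays.

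**What to change.** Pre-specify, as the H2 analysis of prolonged observation, a logistic model with asthma, severity at presentation and baseline covariates only. Keep the model with the epinephrine terms as a secondary, separately labelled analysis. Wherever time to epinephrine is a predictor, count stay from the first dose.

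To make this workable, Section 6 or 7 should state where each clock starts, how pre-hospital doses are handled, and how a prolonged stay is defined. The cut-off itself is for the investigators.

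The cost is SAP wording and one extra model, and the epinephrine odds ratios for stay become secondary. No new data appear to be needed beyond the timestamps behind variables already listed.

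### The only adjusted analysis of observation time uses an undefined yes/no outcome, although durations are recorded and could be modelled directly

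*Combined protocol and SAP*

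**What the plan says.** Section 7 (Regression analysis) plans logistic regression to find "independent predictors of biphasic reactions and prolonged observation", with "candidate variables: time to epinephrine, asthma, severity, multiple epinephrine doses". Section 3 states in H2 that asthma and a severe presentation go with "higher risk of biphasic reactions and prolonged observation requirements". Neither section gives a length of time, a percentile or any other rule that makes observation prolonged, and no other section supplies one.

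The quantity itself is collected. Section 6 lists "Duration of ED observation, hospitalization, ICU stay" among the variables, without a unit, and the primary objective in Section 2 begins "To determine the average observation period in the pediatric emergency department". Apart from descriptive summaries, the only planned use of duration as a quantity is in the unadjusted comparisons: "Student's t-test or Mann-Whitney U test for continuous variables, depending on distribution". No adjusted model of duration is planned.

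The records run from January 2014 to December 2024. The document is dated 3 October 2025.

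**The concern.** Logistic regression needs a categorical outcome, so a recorded duration, or some outcome built from durations, must be split at an unstated point. Two consequences follow for the adjusted analysis.

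First, a split ignores how far each child lies from the cut-off. The sample is fixed at all eligible patients and cannot be enlarged to make up for this.

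Second, the outcomes already exist and the plan names no cut-off, so one could be picked after several have been tried. The bare 0.05 rule in Section 7 does not allow for that, and a second analyst could not reproduce the result from the plan.

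What is at stake is the adjusted evidence for the second half of H2, in a study that Section 9 expects to inform clinical practice on observation.

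**Working it through.** The plan gives no sample size, power, effect size, spread or cut-off, so it has no figure to reproduce. Everything below is an illustration under stated assumptions. The cut-offs in hours serve only the arithmetic and are not suggestions.

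**1. Information kept after a split.** Assume log-duration is normal and a predictor shifts it by a constant. A cut on duration is then a cut on log-duration. The efficiency of a split at quantile q, relative to the full quantity, is φ(z_q)² / [q(1 − q)].

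| Split at | φ(z_q) | φ² | q(1 − q) | Kept | Lost |
|---|---|---|---|---|---|
| median | 0.399 | 0.159 | 0.250 | 0.64 | 36% |
| 75th percentile | 0.318 | 0.101 | 0.188 | 0.54 | 46% |
| 90th percentile | 0.175 | 0.031 | 0.090 | 0.34 | 66% |

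**2. The same loss as sample size.** Assume two equal groups, a 0.5 SD difference, two-sided 5% and 80% power. As a quantity, n = 2(1.960 + 0.842)² / 0.5² = 62.8, so 63 per group. For a yes/no outcome cut at a quantile of the reference group, the pooled two-proportion formula gives:

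| Cut at | Proportions above the cut | n per group | Power with 63 per group |
|---|---|---|---|
| median | 0.500 v 0.691 | 102 | 59% |
| 75th percentile | 0.250 v 0.431 | 107 | 57% |
| 90th percentile | 0.100 v 0.217 | 152 | 44% |

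**3. False positives if the cut-off is searched.** Assume log-normal durations with median 6 h and log-SD 0.7, one binary predictor with no effect and 25% prevalence, and cut-offs at 4, 6, 8, 12 and 24 h, of which the one with the smallest p-value is reported. With the Wald test of a one-predictor logistic model, the false-positive rate is about 13% at N = 100, 15% at N = 200 and 16-17% at N = 400. An uncorrected Pearson or z-test gives roughly 17-19%. One fixed 6 h cut-off stays at about 4-5% with the Wald test, and a t-test on log-duration at about 5%. Under these inputs only 1 − Φ(ln(24/6)/0.7) = 1 − Φ(1.98) = 2.4% of children exceed 24 h, so that cut-off adds little in small samples.

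**4. Which duration to model.** Sicker children may leave the ED early because they are admitted, which makes ED time short when the need for observation is long. In a hypothetical simulation the true duration ratio was 1.35, and 20% of children were admitted at about 3 h, with admission related to the predictor and to unexplained need. A log-linear model of ED time alone returned 1.07. An accelerated failure time model that censored at admission returned 1.27, because the censoring was informative. The choice of duration therefore matters as much as the choice of model.

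**The case against.** The strongest reply is that the defect is only an undefined outcome. One stated definition would remove the error-rate problem, and modelling duration would then be an efficiency preference. Prolonged observation appears in no listed objective; the secondary risk-factor objective concerns biphasic reactions alone. A threshold may also be the natural scale for a study about safe observation periods, and a yes/no outcome that counts admission as prolonged avoids the truncation in step 4.

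Part of this stands. A single definition fixed in advance does deal with cut-off searching, and a yes/no version has a place. It does not recover the lost information in a sample that cannot grow, and the adjusted model is the one from which Section 7 draws its independent predictors.

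Stronger readings are tempting, but the documents do not support them:

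- A reader might infer that every test of the second half of H2 loses power. The planned t or Mann-Whitney comparisons can use duration as a quantity; only the adjusted analysis is affected.
- A reader might infer that the cut-off will be chosen after the fact. No section says that extraction has begun, and the document is dated nine days after ethics approval (24 September 2025). The plan leaves that route open and does not show that it was taken.
- A reader might take prolonged observation to be a split of ED time in hours. H2 speaks of observation requirements, Section 6 gives no unit, and the definition could include admission.
- A reader might put the false-positive rate at 18-19%. That belongs to the uncorrected Pearson or z-test, not to the Wald test of the planned model.

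**Conclusion.** The concern holds for the adjusted analysis. Its outcome is undefined, and the recorded durations allow a better one. The illustrative size is 36% of the information lost at a median split and 66% at the 90th percentile, and about 13-17% false positives per null predictor if the best of five cut-offs were reported.

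That the outcome lacks a definition while durations are recorded rests on the text alone. The percentages rest on assumptions: normal log-durations, a constant shift, and the chosen median, spread, prevalence, sample sizes and cut-offs. Skewed or truncated data would change them. The false-positive figures also assume a search that the plan does not describe. This should be corrected, though it concerns a secondary analysis.

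**What to change.** In Section 7, make the main adjusted analysis a linear regression of log duration on the four candidate variables, and report duration ratios with 95% confidence intervals.

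Define duration so that admission does not shorten it. One option is total observed time from ED arrival to discharge, built from the ED, hospitalization and ICU durations in Section 6, with the unit stated and overlapping periods counted once. Do not rely on ED time alone, or on treating admission as non-informative censoring.

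If the yes/no model is kept, make it secondary. Fix one definition before data extraction, including how admitted children are classified, and use the same definition in H2.

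The cost is SAP wording, with no new variables or patients. Results will read as percent change in duration instead of odds ratios. Total time also includes inpatient stay that may have other causes, so show an ED-only sensitivity analysis beside the main result, with its truncation at admission acknowledged.

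### If time to epinephrine and multiple doses enter the same logistic model, its delay odds ratio leaves out any part of the H1 effect that acts through repeat dosing

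*Combined protocol and SAP*

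**What the plan says.** Section 7 (Statistical Analysis Plan, Regression analysis) plans "Logistic regression to identify independent predictors of biphasic reactions and prolonged observation", followed by a single list: "candidate variables: time to epinephrine, asthma, severity, multiple epinephrine doses". It gives no separate model for each hypothesis, no rule for which candidates are entered or kept, and no mediation analysis.

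Section 3 states H1 as a causal claim: "Early administration of intramuscular epinephrine reduces the risk of biphasic reactions and improves clinical outcomes". It sets no condition on the number of doses and does not say whether a total or a direct effect is meant. H3 is predictive: "Children requiring multiple doses of epinephrine are at increased risk for hospitalization and biphasic reactions".

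The first secondary objective in Section 2 is "To analyze independent risk factors for biphasic reactions, including delayed epinephrine administration, asthma history, and severity at presentation". Multiple doses are not named there. Section 6 records "time to first dose, number of doses" among the treatment variables. Section 7 also plans unadjusted comparisons, including "Student's t-test or Mann-Whitney U test for continuous variables, depending on distribution".

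**The concern.** Asthma and severity at presentation are fixed before treatment. The number of doses is not: a second dose can be given only after the first, and it partly reflects how the reaction responded. If late treatment lets a reaction progress, it may lead to more repeat dosing. If repeat dosing also marks a higher biphasic risk, as H3 proposes, it lies on the path from delay to outcome. Holding it constant takes that path out of the delay estimate. Counting only the doses given for the initial reaction does not change this, because those doses also come after the first.

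Independent predictors most naturally means mutually adjusted ones. Read that way, the plan contains no H1 estimate adjusted for pre-treatment factors alone. The study could report that delay is not an independent predictor partly because of the covariate list, and Section 9 expects the results to guide practice.

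**Working it through.** The documents give no sample size, event count, biphasic rate, repeat-dose rate or effect size, so there is no figure of the plan's to reproduce. **All inputs below are assumptions.** The calculations show how the mechanism works and its possible range, not what this cohort will show.

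**1. Order in time.** Section 6 separates time to the first dose from the number of doses. The first is the H1 exposure, and the second is known only afterwards. Multiple doses is therefore a post-exposure variable in an H1 model.

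**2. Complete mediation, by hand.** Assume a 4% biphasic risk with one dose, an odds ratio of 4 for multiple doses, and no direct effect of delay.
- Risk with multiple doses: odds 0.04/0.96 × 4 = 0.1667, so risk 0.1667/1.1667 = 14.3%.
- Early treatment, 10% with multiple doses: 0.90 × 4% + 0.10 × 14.3% = 5.03%.
- Late treatment, 25%: 0.75 × 4% + 0.25 × 14.3% = 6.57%. With 30%: 7.09%.
- Total odds ratio: (0.0657/0.9343)/(0.0503/0.9497) = 1.33; with 30%, 1.44.
- Within a dose group the odds ratio is 1.00 by construction.
- With an odds ratio of 3 for multiple doses, and 10% versus 20%, the risks are 4.71% and 5.42%. The total odds ratio is 1.16, again against 1.00.

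**3. Range of cases, by exact enumeration.** Large-sample logistic coefficients were computed for delay with asthma and severity, then with multiple doses added. The assumptions were:
- reference risks of 12% for repeat dosing and 4% for biphasic reaction;
- asthma in 25%, with odds ratio 1.5 for biphasic reaction;
- severe presentation in 30%, with odds ratio 2 for both repeat dosing and biphasic reaction;
- delay in 40% of non-severe children, with severe children treated somewhat sooner (odds ratio 0.7 for delay);
- where used, an unmeasured factor in 30%, with odds ratio 3 for both repeat dosing and biphasic reaction.

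Share lost = 1 − ln(OR with doses)/ln(OR without doses), taken before rounding. For example, 1 − ln 1.50/ln 2.03 = 1 − 0.405/0.708 = 43%.

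| Delay→repeat dosing OR | Direct delay OR | Repeat dosing→biphasic OR | Unmeasured cause | Delay OR without doses | Delay OR with doses | Share lost |
|---|---|---|---|---|---|---|
| 1 | 2 | 4 | no | 1.94 | 2.00 | none |
| 3 | 2 | 2 | no | 2.31 | 2.00 | 17% |
| 3 | 2 | 4 | no | 2.66 | 2.00 | 29% |
| 3 | 1.5 | 4 | no | 2.03 | 1.50 | 43% |
| 2 | 1 | 4 | no | 1.22 | 1.00 | 100% |
| 3 | 1 | 4 | no | 1.39 | 1.00 | 100% |
| 5 | 1 | 4 | no | 1.63 | 1.00 | 100% |
| 3 | 1 | 4 | yes | 1.37 | 0.94 | past the null |
| 3 | 1 | 1 | yes | 1.00 | 0.94 | no effect to lose |

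The small rise in the first row reflects the non-collapsibility of odds ratios. The last row isolates the second problem: delay has no effect at all, yet conditioning on repeat dosing moves its odds ratio off 1.

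**4. Effect on power.** This uses a Wald approximation with two-sided 0.05 assumed, because sidedness is not stated. For 2.66 without doses versus 2.00 with them, power is 0.33 versus 0.17 at N = 100, 0.57 versus 0.30 at N = 200, and 0.86 versus 0.53 at N = 400. For the completely mediated 1.39, it is only 0.07, 0.09 and 0.14 even without doses in the model.

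**The case against.** The strongest reply is that the plan does not commit to this adjustment. The variables are only candidates, and no entry rule is given. That stands: the loss occurs if both are entered. Without a rule, though, whether the H1 estimate is adjusted for repeat dosing may depend on the data, which is also a reason to specify the model.

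A reader might infer that the hypotheses themselves describe a chain from delay through repeat dosing to biphasic reaction. They do not. H1 does not mention repeat dosing, H3 does not mention delay, and no section links the two.

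Repeat dosing may also stand in for severity that is poorly captured at presentation. If sicker children are treated sooner, leaving it out can leave confounding in the H1 estimate. This stands too. Neither model is shown to be unbiased, so a flat statement that the plan biases H1 toward no effect would go too far.

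The Section 2 objective asks for independent risk factors, which a mutually adjusted model does answer, and H1 does not specify a total effect. But H1 is worded as an effect of early treatment, not as an effect at a fixed number of doses. The unadjusted comparisons in Section 7 are not conditioned on dose count, but they are confounded by severity and cannot replace an adjusted H1 estimate.

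Finally, the completely mediated effects are small. With n per group = 7.849 × [p₁(1−p₁) + p₂(1−p₂)]/(p₁−p₂)² (80% power, two-sided 0.05), 5.03% versus 6.57% needs 7.849 × 0.1092/0.01543², about 3,600 per group, and 5.03% versus 7.09% about 2,100. Unless the cohort runs to thousands, the better model would usually be non-significant there as well. The case for changing it is that it estimates the right quantity, not that it would rescue significance in that scenario.

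**Conclusion.** The concern holds in conditional form. If time to epinephrine and multiple doses are entered together, the delay odds ratio omits whatever part of the H1 effect acts through repeat dosing, and it may carry bias from unmeasured shared causes. Any direct effect of delay stays in the model. Under the assumed inputs the loss runs from none, through 17–43% of the log odds ratio, to 100%; with an unmeasured shared cause the estimate can pass the null (0.94).

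A reader might infer that the plan erases the H1 effect and that 1.00 is the expected result. The documents do not support that: 1.00 follows from assuming no direct effect, and the path from delay to repeat dosing is neither stated nor quantified. H1 belongs to a secondary objective; the primary results on observation time and on biphasic frequency and timing are not affected. The change should be made because the omission is structural and cheap to mend, although its size in this cohort cannot be known from the documents.

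**What to change.** In Section 7, name the model for each hypothesis before analysis.

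- **H1:** the primary model is time to first epinephrine dose adjusted for pre-treatment factors only (asthma, severity at presentation), without multiple doses.
- **H3, biphasic reactions:** use the four-variable model and interpret the multiple-doses coefficient. Do not read its time-to-epinephrine coefficient as the test of H1; show it beside the H1 estimate as a sensitivity analysis.
- **Prolonged observation:** if time to epinephrine is interpreted for this outcome, use the same pre-treatment-only model.

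The cost is one extra logistic model per outcome and a few sentences in the plan, using variables Section 6 already collects. The downside is that, if severity at presentation is coarsely graded, the H1 model loses a partial proxy for residual severity. Showing both estimates makes that visible.

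### Age and trigger are collected but are not among the candidates for either logistic model, so the asthma and time-to-epinephrine odds ratios may be confounded, by an amount the documents cannot fix

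*Combined protocol and SAP*

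**What the plan says.** Section 7 (Regression analysis) plans "Logistic regression to identify independent predictors of biphasic reactions and prolonged observation", with a single list serving both outcomes: "candidate variables: time to epinephrine, asthma, severity, multiple epinephrine doses".

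Section 6 collects more baseline information than the list uses. Its entries include "Demographics (age, sex" in the demographics line and "Triggers (food, drug, insect sting, idiopathic" in the triggers line. Section 5 admits "Children aged 0–18 years", and Section 4 describes the design as "Retrospective analytic cohort (chart review".

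On purpose, the first secondary objective in Section 2 reads "To analyze independent risk factors for biphasic reactions, including delayed epinephrine administration, asthma history, and severity at presentation". H1 in Section 3 is causal in wording: "Early administration of intramuscular epinephrine reduces the risk of biphasic reactions and improves clinical outcomes". H2 ties asthma history to both outcomes.

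The Comparisons bullet in Section 7 offers only two-group tests. No section plans stratification, matching, a rule for choosing confounders, or a sensitivity analysis involving age or trigger.

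**The concern.** In a chart-review cohort nothing balances baseline factors across exposure groups, so an odds ratio is adjusted only for what is put in the model. Two collected factors are plausible confounders.

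- **Age.** A history of asthma can only build up as a child grows older, so asthma and age are likely to be linked in a cohort that starts at birth. If length of observation or recurrence also varies with age, an asthma odds ratio from a model without age absorbs part of that variation. This bears on H2.
- **Trigger.** The trigger might influence how soon epinephrine is given and might also relate to recurrence. If both hold, the time-to-epinephrine odds ratio in H1 is affected. The documents give no figures for either link.

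Such bias does not shrink as patients are added; the false-positive rate rises instead. Section 9 expects the results to inform practice on observation periods, so an odds ratio labelled independent should be adjusted for the obvious measured baseline factors, or the omission should be explained.

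**Working it through.** The documents give no sample size, event rate or effect size, so there is no figure of theirs to reproduce. **All inputs below are assumptions.** They show what could happen, not what will.

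**1. Mechanism, by hand.** Take two equally sized age bands and no true asthma effect. Asthma prevalence is 3% in the younger band and 25% in the older. Prolonged observation is 25% and 50%.

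- Odds with asthma: (0.03×0.25 + 0.25×0.50) / (0.03×0.75 + 0.25×0.50) = 0.1325/0.1475 = 0.898.
- Odds without asthma: (0.97×0.25 + 0.75×0.50) / (0.97×0.75 + 0.75×0.50) = 0.6175/1.1025 = 0.560.
- Spurious OR = 0.898/0.560 = 1.60. Swapping the two prolonged-observation rates gives 0.60.

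The contrast is deliberately sharp. It shows that the bias can exist and can go either way.

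**2. Continuous age, prolonged observation.** Age is uniform on 0–18. P(asthma) = 0.02 + 0.016×age, which is 2% at birth and 0.02 + 0.288 = 31% at 18. The outcome model is logit P(prolonged) = −0.4 + b×(age − 9), with no asthma term. A logistic model with asthma but not age was fitted to 2,000 simulated data sets per setting. At b = 0.10 the logit runs from −1.3 to 0.5, so prolonged observation goes from 21% to 62%, an odds ratio of exp(1.8) ≈ 6 from birth to 18. At b = 0.05 it runs from −0.85 to 0.05, or 30% to 51%.

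| Age slope b | Asthma OR, age omitted | False positives, N=200 | False positives, N=400 |
|---|---|---|---|
| 0 | 1.0 | about 5% | about 5% |
| 0.025 | 1.07 | 5.4% | not shown |
| +0.05 / −0.05 | 1.17 / 0.85 | 6.7% / 6.1% | 8.7% / 8.5% |
| +0.10 / −0.10 | about 1.35 / 0.74 | about 10–12% | about 18–20% |

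With age in the model at the strong slope, the OR is 0.99–1.01 and the false-positive rate 3.9–4.9%. The ranges in the last row reflect simulation error across repeated runs.

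**3. Biphasic reactions.** With the intercept changed to −2.5 (about 7.6% at age 9) and N=200, omitting age gives false-positive rates of 5.2% at b = 0.05 and 7.3% at b = 0.10. Rare events leave less power to detect a spurious effect. The bias itself remains.

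**4. A general omitted binary factor.** Assume exposure prevalence 20%, event rate 5–15% and a true OR of 1.00.

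- Factor unrelated to the outcome, or equally common in exposed and unexposed: the OR stays 1.00.
- Factor–outcome OR 1.5, prevalence 50% in exposed and 40% in unexposed: 1.04.
- Factor–outcome OR 2, prevalence 60% and 40%: about 1.14.
- Factor–outcome OR 3, prevalence 70% and 30%: about 1.51.

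Nothing in the documents places age or trigger within this range.

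**5. Cost in parameters.** Count one parameter for each of the four listed candidates. Age makes 5. Trigger, with four categories, adds 3 more, making 8. At an assumed 10 events per parameter, the events needed are 40, 50 and 80. At an assumed biphasic rate of 10%, that is N = 400, 500 and 800; at 5% it is 800, 1,000 and 1,600. Age is cheap; trigger is not.

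**The case against.** The strongest objection is that confounding has not been shown. It needs age or trigger to be related to the exposure and to the outcome, given the covariates already in the model, and the documents give no such data. This stands. A reader might infer from the omission that the odds ratios are confounded, or that the higher false-positive rates are to be expected. The documents support neither: those rates need an age odds ratio of about 6 across childhood, and with weaker slopes they fall back towards 5%.

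The simulation is also narrow. It covers asthma and age, mainly for prolonged observation, and leaves out severity, epinephrine timing and number of doses, which might carry part of any age effect. Nothing was computed for trigger or for the time-to-epinephrine odds ratio. This stands too, and that part of the point rests on reasoning alone.

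It can be said that the list names candidates and does not forbid further terms. That is possible, but it has no wording to suggest examples, whereas the normality bullet in the same section does. If more terms are intended, the plan should say so.

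Finally, extra terms could overfit. With no event count stated, this is a fair objection to forcing three trigger parameters into the biphasic model. Nor can one assume that the prolonged-observation model has ample events, because the plan gives no cut-off for prolonged. The objection has little force against one parameter for age.

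**Conclusion.** The point holds as a gap in specification. Two measured potential confounders are missing from the only covariate list, without a reason, in a non-randomised study that aims at independent predictors and words H1 causally. The asthma and time-to-epinephrine odds ratios may be confounded; direction and size are unknown.

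For age, under the set-up in step 2, the spurious asthma odds ratio for prolonged observation lies between about 1.0 and about 1.35 or 0.74. The false-positive rate lies between about 5% and 12% at N=200, and reaches about 20% at N=400. These figures rest on an assumed age–asthma gradient, assumed age slopes, assumed sample sizes and a model without the other three candidates. They are not bounds: the sharper contrast in step 1 gives more, and no age effect gives nothing. The case for adding age is clear because the change costs so little. The case for trigger is weaker and depends on the number of events.

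**What to change.** Amend the Regression analysis bullet in Section 7 as follows.

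- Enter age in years as a continuous term in both models, and keep it whatever its p-value.
- Add trigger to the prolonged-observation model if the number of events allows, with that condition stated in advance.
- In the biphasic model, use trigger only in a stated sensitivity analysis, with a penalised (for example Firth) fit or collapsed categories.
- State the expected number of events for each outcome so that these choices can be judged. If age or trigger is left out, give the reason.

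Both variables are already on the collection list, so this is a change of wording with no new data. The price is one parameter for age and up to three for trigger, with somewhat wider intervals, chiefly in the biphasic model if events are few.
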